## 2 INTRODUCTION

Nicotine replacement therapy (NRT) is the most widely used pharmacological therapy for smoking cessation. One of the widely used NRTs is nicotine transdermal system, which is also known as nicotine transdermal patch. The impacts of the change of the manufacturing site will be tested in this bioequivalence study.

### 2.1 Study Rationale

NicoDerm CQ patch is manufactured by Alza. GSK will submit an application to support the change of manufacturing site from Alza to Dungarvan.

The purpose of this study is to assess the bioequivalence of the 21 mg nicotine transdermal patch from GSK Dungarvan (Test) compared to the 21 mg nicotine transdermal patch currently manufactured by Alza (Reference).

### 2.2 Background

Nicoderm CQ patch is a marketed formulation for which the pharmacokinetics, efficacy and safety has been demonstrated in clinical studies and post marketing data.

### 2.3 Benefit/Risk Assessment

Complete information for this product may be found in the single reference safety document (SRSD), which for this study is the US prescribing information (OTC Drug Facts label & Package Insert).

### 2.4 Mechanism of Action/Indication

Nicotine replacement therapy (NRT) has proven to be an effective aid to smoking cessation by reducing nicotine withdrawal symptoms associated with smoking cessation.

## 3 STUDY OBJECTIVES AND ENDPOINTS

**Table 3-1 Study Objectives and Endpoints**

Objectives	Endpoints
Primary	
Demonstrate the bioequivalence of the 21 mg nicotine transdermal patch from GSK Dungarvan (Test) compared to the 21 mg nicotine transdermal patch manufactured by Alza (Reference)	
 
<math>C_{max}</math> (The maximum observed post-dose concentration; obtained without interpolation)
 
<math>AUC_{0-t}</math> (The area under the plasma concentration versus time curve calculated from time 0 to the last measurable sampling time point, t, computed using the linear trapezoidal rule)
 

	
 
AUC0-inf (The area under the plasma concentration versus time curve calculated from time 0 to infinity)
 

Secondary	
Pharmacokinetics	
Assess the pharmacokinetic profile of the patches	
 
<math>\lambda_z</math> (The terminal elimination rate constant)
 
<math>t_{max}</math> (The time of the maximum observed post-dose concentration)
 
<math>t_{1/2}</math> (The elimination half-life computed as <math>t_{1/2} = \ln(2) / \lambda_z</math>)
 

Adhesion	
To monitor adhesion of the patches to the skin	Adhesion score
Safety	
Assess the safety profile (local and systemic) of both products	
 
Monitoring and recording of adverse events
 
Physical examination
 
Vital signs
 
Laboratory tests
 

This study will be considered successful if bioequivalence between the Test and Reference treatments conclude that the 90% confidence intervals for the ratio of the means of the primary pharmacokinetic parameters AUC0-t and AUC0-inf and Cmax of the nicotine profiles lie completely within the range 0.8-1.25.

## 4 STUDY DESIGN

### 4.1 Overall Design

This is a 2-arm, single center, single dose, open-label, randomized, two-sequence, two-period crossover, bioequivalence study in healthy adult smokers that have smoked more than 10 cigarettes per day for 1 year prior to inclusion.

Subjects will be randomly assigned to receive a single-dose of one of the following treatments which will follow a cross-over design:

Treatment A: 21 mg/24h NicoDerm CQ (GSK Dungarvan)-Test

Treatment B: 21 mg/24h NicoDerm CQ (Alza)- Reference

In each treatment period, each subject will be dosed once, i.e., a single NicoDerm patch will be placed under fasted conditions to the upper part of the back for a total duration of 24 hours, and then removed. Blood will be sampled regularly at scheduled times for 36 hours following patch application. The pharmacokinetic profile may be altered when a patch loses its adherence to the skin. Therefore, the adhesion of the patch should be monitored. Adhesion will be assessed five times: immediately after patch application, approximately 6, 12 and 18 hours after application and immediately prior to patch removal.

Carry-over effects will be avoided by a wash-out interval of at least 2 days (but no more than 4 days) from patch removal in the first treatment period to subsequent patch application.

The study will consist of an ambulant screening day within 21 days prior first patch application. Subjects will be confined in the study facility from 48 hours pre dosing and for 36 hours post last dosing; pharmacokinetic (PK) blood samples will be obtained at predose (within 1 hour before dosing), 30 minutes and 1, 2, 3, 4, 5, 6, 8, 10, 12, 14, 16, 18, 20, 24, 25, 26, 27, 28, 30, 32, and 36 hours after administration of the patch.

For each subject the duration of study participation is 27 days of which up to 8 days confined.

Subjects are to abstain from smoking during the confinement period and be subject to random measurements of expired carbon monoxide (CO) to confirm abstinence. The CO levels must be  $\leq 10$  ppm throughout the study.

Procedures must be in place to avoid nicotine cross-contamination i.e. all staff members at the clinical site and the bioanalytical laboratory who are involved in this study must not use any tobacco or nicotine containing products to avoid nicotine cross-contamination.

## 4.2 Scientific Rationale for Study Design

The reported plasma  $t_{1/2}$  for nicotine is approximately 1 to 4 hours in a heterogeneous population such as the US. The 48-hour smoking restriction period prior to dosing will therefore minimize the residual nicotine amount from smoking during previous furlough.

This will be an open label study. Blinding is not considered essential as study measurements (blood nicotine concentrations) are biological. A crossover design, using the same subjects to test each product, will be used to reduce variability.

The blood sampling times have been chosen based on the information available particularly on nicotine absorption, as well as its elimination.

Smokers have been chosen as the population for this study as they are the population that the investigational product would target, if marketed.

The following guidance have been followed for designing the study:

- US-FDA's recommendations for BE/PK studies with transdermal nicotine products ([FDA Guidance on Nicotine 2019](#))
- Draft guidance Bioequivalence Studies with Pharmacokinetic Endpoints for Drugs Submitted Under an Abbreviated New Drug Application ([FDA 2013](#))
- US-FDA's recommendations for assessing adhesion with transdermal delivery systems and topical patches for Abbreviated New Drug Applications products ([FDA 2018](#))

## 4.3 Justification for Dose

This is a study to assess the bioequivalence of the test product to a commercial reference product. The transdermal system will be applied to the back and worn for 24 hours.

## 4.4 End of Study Definition

The End of Study is defined as the date of the last visit of the last subject to complete the study.

A subject is considered to have completed the study if he or she has completed all phases of the study including the last visit or the last scheduled procedure shown in the Schedule of Activities.

## 5 STUDY POPULATION

### 5.1 Type and Planned Number of Subjects

A sufficient number of subjects will be screened to randomize approximately 20 to ensure at least 12 evaluable subjects complete the entire study.

An enrolled subject is one who has agreed to participate in the clinical study following completion of the informed consent process directly or via their legally authorized representative and successfully met eligibility criteria to proceed beyond the screening visit as applicable for the protocol design.

This study can fulfill its objectives only if appropriate subjects are enrolled. The following eligibility criteria are designed to select subjects for whom participation in the study is considered appropriate. All relevant medical and non-medical conditions should be taken into consideration when deciding whether a subject is suitable for this protocol.

Subject eligibility to participate in the clinical study should be reviewed and documented by an appropriate member of the investigator's study team before subjects are included in the study.

### 5.2 Inclusion Criteria

An individual must meet all the following inclusion criteria to be eligible to be included into the study:

1. Subject provision of a signed and dated informed consent document indicating that the subject has been informed of all pertinent aspects of the study before any assessment is performed.
2. Subject is male or female. An effort will be made to include similar proportions of males and females in the study.
3. Subject is 21 to 55 years of age inclusive, at the signing of the informed consent
4. Subject is willing and able to comply with scheduled visits, treatment plan, laboratory tests, and other study procedures.
5. A subject in good general and mental health with, in the opinion of the investigator or medically qualified designee, as determined by medical evaluation, including a detailed medical history, full physical examination, including blood pressure and pulse rate measurement, 12-lead ECG or clinical laboratory tests.
6. Body Mass Index (BMI) of 19 to 27 kg/m^2; and a total body weight >50 kg (110 lbs).
7. Any female subject of childbearing potential and at risk for pregnancy must agree to use a highly effective method of contraception throughout the study and for at least 5 days after the last dose of assigned treatment. Female subjects who are not of childbearing potential must meet requirements in [Section 5.4.4](#) of protocol.
8. Subject admits to having smoked more than 10 cigarettes per day for the preceding one year (prior to initial dose).
9. Subject with two negative tests (one at screening and one at check in Day-2) for active COVID-19, separated by > 24 hours.

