**Footnotes:**

\* These assessments are also to be conducted for subjects who discontinue study drug. End of Study visit will occur before discharge, on study Day 6

a Including site application examination; full physical examination at screening and final visit and examination of the areas on the back only before each patch application

b Including body temperature; body temperature will be measured every day; all vital signs will be assessed at screening, pre-treatment in each treatment period (1 – 30 minutes before drug administration) and final visit.

c PK blood samples will be collected at predose (within 1 hour before dosing) and at 30 minutes and at 1, 2, 3, 4, 5, 6, 8, 10, 12, 14, 16, 18, 20, 24, 25, 26, 27, 28, 30, 32, and 36 hours after administration of the patch. See [section 8.2](#)

d Within 5 minutes from patch application and approximately 6, 12, 18 hours post application and before patch removal (24 hours after patch application)

e At the discretion of the Investigator, the subjects could continue the study if any deviation to the inclusion/exclusion criteria does not anticipate to alter study integrity.

f Adverse Events (AEs) and therefore all Serious Adverse Events (SAEs) will be collected immediately after a subject provides consent to participate in the study by the completion of the Informed Consent Form (ICF).

g Breath CO measurement taken upon check-in, on day -2 and immediately prior to randomization in Period 1, immediately prior to dosing in Period 2, one during the wash-out, 3 times randomly in each period and immediately after the last PK sample in each period.

h Before dosing two consecutive approved (Locally approved tests (PCR or Antigen) will be performed: one test at screening and one test at check-in (Day-2). If the second test is > 72 hours prior to unit admission, subjects should be advised to self-quarantine until entrance to the unit while awaiting final testing clearance. Subjects who report symptoms suggestive of COVID-19 while in the research unit should be isolated in the unit or at home and tested for COVID-19 infection using an approved molecular test. One test (Locally approved tests (PCR or Antigen) should be performed before releasing the subject from the unit i.e. at early discontinuation or end of study.

i Includes Smoking history

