### 8.1.6 Screening Procedures

The following procedures will be completed:

- Obtain written informed consent and record in the CRF.
- Review Inclusion and Exclusion criteria and record in the CRF.
- Collect demography, including year of birth, gender, ethnicity and race and record in the CRF.
- Collect height and weight. The results for each measurement will be recorded in the CRF.
- Obtain medical history as related to the inclusion/exclusion criteria, including any relevant medical or surgical history, allergies or drug sensitivity, history of illegal drug and alcohol use. Significant findings that are present before consent must be included in the CRF.
- Collect smoking habits, including number of cigarettes smoked per day and record in the CRF.
- Obtain complete medication history of all prescription or nonprescription drugs, and dietary and herbal supplements taken within 90 days prior to consent, and record in the CRF.
- Obtain supine blood pressure (BP), pulse rate (PR), respiratory rate and oral body temperature. The results for each measurement will be recorded in the CRF.
- Conduct full physical examination and skin site application evaluation. Any clinically relevant findings will be noted in the AE CRF page and enrollment will be based upon investigator judgement.
- Contraceptive review.
- Collect nasopharyngeal swab sample for COVID19 test. Date and time of sample collection and test results (positive or negative) will be documented in the CRF.
- Collect single 12 lead electrocardiogram (ECG). Results (normal or abnormal) and clinical significance will be recorded on the CRF.
- Following at least a 4 hour fast, collect blood and urine specimens for the following, and recorded on the CRF:
  - Safety laboratory tests and virology;
  - Urine drug screening;
  - Alcohol screening;
  - Serum FSH concentration for any female who has been amenorrheic for at least 12 consecutive months;
  - Serum  $\beta$ -hCG for all females of childbearing potential.
- Spontaneous reporting of adverse events and those elicited by asking subjects to respond to a non-leading question such as “How do you feel?” will be assessed and any AEs recorded in the CRF.

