#### 9.2.1 Laboratory Tests

The following laboratory tests/analytical measures will be performed by appropriately trained staff/clinical examiners, at the times and in the order defined in the [Study Procedures](#) of this protocol.

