**Table 9-1 Laboratory Tests**

Hematology	Chemistry	Urinalysis	Other
Hemoglobin	BUN/urea and Creatinine	pH	Urine drug screen b
Hematocrit	Glucose (fasting)	Glucose (qual)	Urine cotinine screen
RBC count	Calcium	Protein (qual)	Serum FSH c
MCV	Magnesium	Blood (qual)	Serum pregnancy test (WCBP) d
MCH	Sodium	Ketones	Urine pregnancy test (WCBP) d
MCHC	Potassium	Nitrites	breath alcohol test
Platelet count	Chloride	Leukocyte esterase	
MPV	Total CO 2 (Bicarbonate)	Urobilinogen	
WBC count	AST, ALT	Urine Bilirubin	
Total neutrophils (Abs)	Direct Bilirubin	Specific gravity	
Eosinophils (Abs)	Indirect Bilirubin	Microscopy a	
Monocytes (Abs)	Total Bilirubin		
Basophils (Abs)	Alkaline phosphatase		
Lymphocytes (Abs)	Uric acid		
	Albumin		

Hematology	Chemistry	Urinalysis	Other
	Total protein		
	AST, ALT (repeat) Total bilirubin (repeat) Albumin (repeat) Alkaline phosphatase (repeat) Direct bilirubin Indirect bilirubin Creatine kinase GGT PT/INR		

Definitions: RBC= Red blood cell; MCV= Mean corpuscular volume; MCH= Mean corpuscular hemoglobin; MCHC= Mean corpuscular hemoglobin concentration; MPV= Mean platelet volume; WBC= White blood cells; BUN=Blood urea nitrogen; HIV= Human immunodeficiency virus; AST= transaminase; ALT= alanine transaminase; PT/INR= prothrombin time/ international normalized ratio; GGT= Gamma-glutamyl transpeptidase.

a Only if urine dipstick is positive for blood, protein, nitrites or leukocyte esterase.

b Minimum requirement for drug testing includes: cocaine, THC, opiates/opioid's, benzodiazepines, 3,4-methylenedioxy-N-methylamphetamine (MDMA)/ecstasy, methamphetamine and amphetamines; to be done as described in [Study Procedures](#)

c FSH done at Screening only in females who have been amenorrhoeic for 1 year.

d WCBP= Female subjects of childbearing potential will be tested for serum human chorionic gonadotropin (hCG) as applicable -see [section 9.2.5](#)

Additional laboratory results may be reported on these samples because of the method of analysis, or the type of analyzer used by the clinical laboratory; or as derived from calculated values. These additional tests would not require additional collection of blood. Unscheduled clinical labs may be obtained at any time during the study to assess any perceived safety concerns.

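### Smoker status at entry rests on self-report: the listed urine cotinine screen is named at no visit and read by no criterion, and the passages on the scope of the 10 ppm CO limit need reconciling

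*Protocol*

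**What the plan says.** Protocol 4.2 explains the choice of population: "Smokers have been chosen as the population for this study as they are the population that the investigational product would target, if marketed". Inclusion 8 in Protocol 5.2 puts this into effect: "Subject admits to having smoked more than 10 cigarettes per day for the preceding one year (prior to initial dose". Screening adds an interview item in 8.1.6: "Collect smoking habits, including number of cigarettes smoked per day and record in the CRF".

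Two objective measures appear in the protocol.

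- **Cotinine.** Table 9-1 has the entry "Urine cotinine screen", with no footnote, timing or cut-off. Section 9.2.1 says the tests in that table are done "at the times and in the order defined in the" Study Procedures section.
- **Expired CO.** Footnote g to Table 1-1 reads: "Breath CO measurement taken upon check-in, on day -2 and immediately prior to randomization in Period 1". Section 4.1, like the synopsis, says CO must be at or below 10 "ppm throughout the study". Section 6.7 gives the purpose of the CO readings as monitoring compliance with the smoking restriction.

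**The concern.** The study is meant to enroll established smokers, yet the criterion that defines them can be met by what the volunteer says. The one listed test that could support that statement has no named visit and no consequence. The other objective reading, CO, is used only to show that subjects are not smoking.

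A volunteer who does not use nicotine regularly could therefore enter on a statement and be scheduled for two 21 mg/24 h patches. At stake are the protection of that subject and whether the enrolled group is the population the protocol says it wants.

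The CO limit raises a second question. Abstinence is required only from check-in, so a compliant smoker may smoke up to admission. It is not clear whether the 10 ppm ceiling then applies to the reading taken at admission.

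**Working it through.** **1. What supports inclusion 8.** The sources are the criterion itself, the smoker history in Protocol 8.1.4 and the smoking habits in 8.1.6. All three record what the subject reports. The eligibility review in 8.1.5 works from the criteria, medical history and prior medications, and adds no measurement of smoking.

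**2. Tracing the cotinine screen.** The column headed Other in Table 9-1 has six entries. Compared with Section 8 and Table 1-1:

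- Urine drug screen: named in 8.1.6 and 8.2.1; own row in Table 1-1; consequence of a positive result in 9.2.3.
- Breath alcohol test: alcohol screening in 8.1.6, breath test in 8.2.1; own row; consequence in 9.2.4.
- Serum and urine pregnancy tests: named in 8.1.6, 8.2.1, 8.2.6 and 8.3; own row; consequence in 9.2.5.
- Serum FSH: named in 8.1.6; no own row, but a footnote to Table 9-1 fixes it at screening, and 5.5.4 uses the result.
- Urine cotinine screen: not named in Section 8; no own row; no footnote; no subsection; no criterion in 5.2 or 5.3 uses it.

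The SAP does not mention cotinine in its drug and alcohol screens (8.4) or its laboratory lists (10.3). Cotinine is the only one of the six with neither a named visit nor a use.

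**3. CO as evidence of smoking.** No lower limit is set anywhere in either document, so a low CO never counts against smoker status.

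**4. Scope of the 10 ppm ceiling.** The passages, side by side:

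- Synopsis and 4.1: throughout the study.
- Exclusion 9 (5.3): immediately before randomization in the first session and before dosing in the second.
- 7.1, repeated in SAP 5.4: any time in the 36-hour post-dose period.
- 8.2.1: the Day -2 result is recorded, with no action stated.
- 9.5, repeated in SAP 10.2: check-in is among the scheduled readings. One action rule covers the reading just before randomization, the other covers values out of limits during the study.

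Exclusion 9 starts abstinence at check-in. Section 5.5.2 asks for at least 48 hours before dosing, and 8.2.1 admits subjects at least 48 hours before dosing, so these agree. Whether the ceiling reaches the check-in reading depends on which passage is followed.

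**5. Size.** The plan's own number reproduces: 12 / (1 − 0.40) = 20 randomized (Protocol 12.1, SAP 5.2). Losses allowed: 20 − 12 = 8. One misreporting subject is 1/20 = 5% of those randomized. The PK population in 12.2 requires both periods, so a withdrawal after Period 1 uses one of the 8.

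**6. Effect on the primary comparison.** With the stated CV of 13%, the within-subject SD on the log scale is √ln(1 + 0.13²) = 0.129. The standard error of the log ratio with 12 subjects is 0.129 × √(2/12) = 0.053. Simulated power for a 90% CI within 0.80 to 1.25 at n = 12 is 97.7%, 91.6% and 66.5% at assumed true ratios of 1.00, 0.95 and 0.90. The plan's own power statement is redacted, so these figures are context only. Nothing in this point changes them.

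**The case against.** **The generic row covers cotinine.** Table 1-1 has a laboratory-tests row marked at screening and end of study, Table 9-1 carries the same title, and 8.1.6 collects urine at screening. Many Table 9-1 analytes are named individually at no visit and will plainly be run. This stands in part: a reader might infer that the cotinine screen would never be done, and the documents do not support that. It does not rescue the criterion, because no rule uses the result even if the test is run.

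**The check-in CO is only a baseline record.** Exclusion 9, 7.1 and 8.2.1 are narrower than the general sentence in 4.1, and 9.5 itself calls the check-in reading a baseline one. A reader might infer that the ceiling turns current smokers away at admission while passing non-smokers. That requires the general sentence and the during-study rule in 9.5 to override the specific ones, and the text does not settle it. What stands is an inconsistency of scope.

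**A positive cotinine does not verify inclusion 8.** Correct: it shows recent nicotine exposure, not more than 10 cigarettes a day for a year. History would still carry the amount and duration, and the investigator keeps discretion under exclusion 27. The test supports the criterion but does not replace it.

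**The result is unaffected.** Each subject receives both patches, so a misreported smoker does not by itself bias the test/reference ratio. This stands in full.

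**How often would it happen?** A reader might assume a misreporting rate. At 2%, the chance of at least one among 20 is 1 − 0.98²⁰ = 33%; at 10%, it is 1 − 0.90²⁰ = 88%. Neither rate comes from the documents, and the result is the chance of a misreporter, not of harm, withdrawal or a wrong conclusion. It should not be used to size the problem.

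**Conclusion.** The gap is real and limited. Smoker status depends on self-report; the listed cotinine screen is named at no visit and tied to no decision; no CO floor exists. So nothing objective supports smoker status before nicotine is applied. This concerns subject protection and fidelity to the stated population. It is not a threat to the bioequivalence conclusion.

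Per misreporting subject, the size is 5% of those randomized, up to two 21 mg/24 h patches, and one of 8 allowed losses if that subject withdraws. The documents give neither the number of such subjects nor any figure for tolerability in people who do not use nicotine, so no overall rate is claimed.

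The differing scope of the 10 ppm limit is a separate inconsistency that the sponsor must resolve. A small, inexpensive change to the entry procedures is worth making.

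**What to change.** 1. Name the urine cotinine screen at Visit 1 in Table 1-1 and in 8.1.6, on the urine already collected there for the drug screen.
2. Add to inclusion 8 that a positive result at the kit's cut-off is required in support of the reported smoking history, and list the result in the SAP with the other screening tests.
3. Reconcile the synopsis, 4.1, exclusion 9, 7.1, 8.2.1 and 9.5 (with SAP 5.4 and 10.2) on which CO readings the 10 ppm limit covers, and state whether it applies to the Day -2 check-in reading. Which rule to adopt is for the sponsor and investigator.

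Cost: one dipstick per screened subject for a test already listed, and wording changes. A few volunteers would fail screening, and 5.6 does not allow them to be re-screened. The test will not confirm daily amount or duration of smoking.
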